Pharmacokinetic profile and dermatomal coverage of the erector spinae plane block - a comparison of bolus dosing and continuous infusion

Principal investigator: [name]., Assistant Professor, Virginia Commonwealth University Department of Anesthesiology

NCT number: not yet available

IRB approval date: March 6, 2019

Date of document: March 7, 2019

Introduction

Background

Muscle plane blocks are a fairly new regional anesthesia technique and are increasing in popularity. The most recent muscle plane block, termed the erector spinae plane (ESP) block, was developed to optimize pain control for thoracic surgery while minimizing the risks associated with paravertebral and epidural blocks. Numerous case reports have advocated for its use¹⁻⁴.

Significance of the research

In comparison to traditional neuraxial and peripheral nerve block approaches, a successful ESP block requires a higher volume of local anesthetic. Therefore, the optimal volume to produce analgesia from an ESP block may result in a plasma local anesthetic concentration that approaches toxic levels. Pharmacokinetic studies have been performed with muscle plane blocks, such as the quadratus lumborum block and transversus abdominus plane block^{5,6}; however, the pharmacokinetic profile of the ESP block has not yet been measured or studied. This study will demonstrate how quickly and closely toxic levels are reached when a routine dose of ropivacaine is given for the ESP block and will also assess for areas of numbness created by the ESP block when routine doses are administered.

Specific aims of the project

- Create plasma ropivacaine concentration-time curves after performance of an ESP block via bolus and continuous infusion into the ESP compartment. The concentration-time curves will include the peak serum concentration of ropivacaine (C_{max}) and the time required to reach maximum plasma concentration (T_{max}).
- Determine the dermatomal distribution and duration of analgesia created when ESP block is performed via ropivacaine bolus versus continuous ropivacaine infusion.

Methods

Study design

This study will use clinical laboratory tests to objectively measure serum ropivacaine levels after an erector spinae plane (ESP) block is performed on patients undergoing cardiac surgery. During an ESP block, ropivacaine is typically injected into a muscle plane that is deep to the erector spinae muscle and superficial to the transverse process of the thoracic vertebral body; subsequently, the ropivacaine is absorbed into the bloodstream, at which time measurements can be taken. Secondary measurements will include distribution and duration of numbness created by the ESP block.

Description of procedures

The ESP block procedure - participant consent will be performed on the day of surgery by one of the research investigators in the pre-operative surgical unit (PSU). Randomization is not required because all participants will be undergoing the same protocol. All participants will also be undergoing cardiac surgery by the same surgeon. Routine care will be performed for the placement of the ESP block and is described as follows: the ESP block will be performed by the acute pain service, which will have members that are not involved with the research. Adequate block placement will be confirmed by one of the investigators via ultrasound images that are captured during the procedure. The participant, who is already in a patient gown with an intravenous line (IV) in place, will be positioned sitting on the side of the patient bed. Vital sign monitoring with pulse oximetry and blood pressure cuff will be connected. The participant will be given intravenous midazolam to reduce anxiety and enhance comfort during the ESP block procedure. Full aseptic precautions will be taken with personal protective equipment and bactericidal preparation with chlorhexidine. An ultrasound probe will be placed lateral to the patient's upper back and the ideal location of medication injection will be identified on an ultrasound image (which is superficial to the transverse processes of the thoracic vertebral bodies and deep to the erector spinae muscle). The skin will be made numb with lidocaine prior to insertion of a larger needle (Tuohy needle); the proceduralist will direct the Tuohy needle to the desired target under ultrasound guidance and 25 cc 0.25% ropivacaine will be delivered through that needle. A continuous nerve catheter will then be inserted through the Tuohy needle to allow for continuous delivery of medication if desired. The Tuohy needle will be removed, and the nerve catheter will be secured in place with adhesive dressing. Cardiac surgery will require bilateral (left and right) nerve catheter placement, and therefore, upon completion of one side, the ESP block will be performed on the other side. The estimated time needed for a bilateral ESP block procedure is 30 minutes. After the completion of the ESP block procedure, the participant will undergo their planned cardiac surgery procedure, which typically takes many hours.

Initiation of continuous nerve catheter infusions (alteration of standard care) - this component of care will be different than routine care. Nerve catheter infusions are typically initiated at the end of the surgical procedure at a concentration and rate of 0.2% ropivacaine at 8-10 cc/hr.

The study protocol will direct the nerve catheter infusions to run at 1 cc/hr; this rate will allow the nerve catheters to remain open and patent but will not significantly interrupt or alter the quality of the research data collection. The operating room team and ICU staff will be notified about the patient's participation in the study and will have information available regarding the alterations from routine practice that would be required for this study.

Research protocol, part 1 - the research protocol and data collection will begin on the afternoon of post-operative day 1 (the day after surgery) in the cardiac surgery intensive care unit (CSICU). Typically, cardiac surgery patients will be sedated and have a breathing tube in place until the morning of post-operative day 1. This delayed timing of the study will allow the participant to stabilize after removal of the breathing tube. Although written consent has already been obtained, a research investigator will obtain a verbal reaffirmation from the participant and update the CSICU team before proceeding.

Per routine, the participant will have vital sign monitors connected and have an arterial line in place that will allow for collection of blood samples for laboratory testing. The nerve catheter infusions will be suspended and the research protocol will begin in the CSICU as follows: the investigator will administer 25 cc 0.25% ropivacaine through each nerve catheter (totaling 50 cc 0.25% ropivacaine) and record the time of administration on a data collection sheet. Either the investigator or study assistant will collect arterial blood samples at the following intervals after the medication bolus: 10 minutes, 15 minutes, 30 minutes, 45 minutes, 60 minutes, 90 minutes, 2 hours, and 4 hours. The blood samples will be labeled with a patient ID sticker and will also contain the study ID number and the time interval that corresponds with the blood sample. The samples will be stored in a designated ice cooler that will be delivered to the clinical laboratory.

During this first portion of sample collection, the secondary outcome of dermatomal analgesia and duration will be assessed. At the 60-minute interval, a study investigator will test areas of numbness performing a pinprick test and using a dermatomal map to mark the areas of numbness. For the pinprick test, the investigator will use a pointed object that is sharp enough to elicit a sharp sensation but blunt enough that it does not cause skin damage; the participant will be asked to provide comparison of the sensation of the pointed object when it is applied to an area that is not expected to be numb (like the palm) versus an area that is expected to be numb (like the chest and thorax). At the 90-minute, 2 hour, and 4 hour intervals, the participant will be asked if the numbness from the nerve block has gone away. If the resolution of numbness occurs between the time intervals, the participant will be asked to look at the clock and remember the time at which the difference was felt. It is expected that at the 4-hour interval, the serum ropivacaine level will be approaching or have reached the baseline level before the bolus was given.

Research protocol, part 2 - at the 4-hour interval (4 hours after the initial bolus), both nerve catheter infusions will be resumed at a concentration and rate of 0.2% ropivacaine at 10 cc/hr. Either the investigator or study assistant will collect arterial blood samples at the following intervals after the start of the infusion: 60 minutes, 2 hours, 4 hours, 8 hours, 12 hours, 24

hours. Dermatomal analgesia assessment will be performed by one of the research investigators at the 24-hour mark. After this assessment, the research protocol will be considered complete and routine care by the CSICU and acute pain service will resume. The researchers will collaborate with the health care teams during the study protocol if this becomes necessary to maintain patient safety and comfort.

The collected blood samples are viable for one week if they are refrigerated and one month if they are frozen. Free and total ropivacaine levels will be determined for each sample by the clinical laboratory and this information will be distributed to the research investigators in a way that protects patient health information and will be recorded securely onto a data collection sheet. The data for this sheet can then be used for statistical analysis and creation of a pharmacokinetic profile for the ESP block (both bolus and infusion curves).

Data analysis

A two-sample Kolmogorov-Smirnov test will be used to determine the difference between the distributions of the bolus arm and the infusion arm. T_{max} and C_{max} of the two arms will be analyzed with an unpaired t-test. A logrank test will be used to assess the difference between the duration of analgesia created by the bolus arm and the infusion arm.

Institutional board approval

The protocol has been approved by Virginia Commonwealth University Institutional Review Board (Study ID HM20014803).

Literature cited

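### One cohort gets the bolus and then the infusion in a fixed order, but the plan tests them as independent arms, so a difference cannot be attributed to regimen

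*Combined protocol and SAP*

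**What the plan says.** The title announces "a comparison of bolus dosing and continuous infusion". The first specific aim is descriptive: to construct concentration-time curves for bolus and infusion, with C_max and T_max. The second is comparative: dermatomal distribution and duration of analgesia "when ESP block is performed via ropivacaine bolus versus continuous ropivacaine infusion".

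Under Description of procedures, the paragraph on the ESP block procedure says "Randomization is not required because all participants will be undergoing the same protocol". The protocol that all participants share is a fixed sequence:

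- Research protocol, part 1: "the research protocol and data collection will begin on the afternoon of post-operative day 1", and "the investigator will administer 25 cc 0.25% ropivacaine through each nerve catheter (totaling 50 cc 0.25% ropivacaine". Sampling runs from 10 minutes to 4 hours. Numbness is mapped at 60 minutes, and its disappearance is asked about at 90 minutes, 2 hours and 4 hours.
- Research protocol, part 2: "at the 4-hour interval (4 hours after the initial bolus), both nerve catheter infusions will be resumed", and the infusions are "resumed at a concentration and rate of 0.2% ropivacaine at 10 cc/hr". Sampling runs from 60 minutes to 24 hours. Numbness is assessed once, at 24 hours.

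In Data analysis, a two-sample Kolmogorov-Smirnov test "will be used to determine the difference between the distributions of the bolus arm and the infusion arm". C_max and T_max are compared by an unpaired t-test, and duration of analgesia by a logrank test. There is no alternate order, no period or carryover term, and no statement that the contrast is descriptive.

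**The concern.** The reason given for not randomising is that there is one group. The analysis then treats that group's two phases as two arms.

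1. **Attribution.** All bolus data come from the first phase and all infusion data from the second. Anything that changes over that time moves with regimen: recovery after surgery, drug handling, or drug left from the bolus. A difference reported as bolus versus infusion could not be assigned to regimen.
2. **Standard error.** The two-sample Kolmogorov-Smirnov, unpaired t and logrank tests assume independent groups. Here each patient contributes to both sides, so the stated uncertainty would be wrong even if no attribution were claimed.

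The comparative aim and every test in Data analysis are at stake. The first aim is not.

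**Working it through.** The documents give no sample size, alpha, effect size or SD, so there is no planned figure to reproduce. Values marked as assumed below are illustrations.

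**1. Can a regimen effect be separated from a period effect?** Write each patient's two results as patient + regimen + period. Under the fixed sequence, regimen equals bolus exactly when period equals 1, so the two columns are identical. With an illustrative n = 20, the matrix has 20 + 1 + 1 = 22 columns, rank 21, and a correlation of 1.0 between regimen and period. No adjustment can separate them. The result does not depend on n or on any pharmacokinetic assumption.

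**2. Does pairing alone cure it?** No. In a simulation with no regimen effect, an assumed within-patient correlation of 0.5, an assumed period effect of 0.5 SD and two-sided 5% tests, the rejection rates were:

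| n (assumed) | Planned unpaired t | Paired t |
|---|---|---|
| 10 | 11.8% | 29.6% |
| 20 | 28.5% | 57.0% |
| 30 | 47.2% | 75.8% |

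A paired test is more sensitive, so it detects the period effect more often.

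**3. What does the unpaired test do to the error?** With common SD s and within-patient correlation r, the variance of the difference in means is 2s²(1 − r)/n, but the unpaired test uses about 2s²/n. Its standard error is too large by the factor 1/√(1 − r): 1.15, 1.41 and 2.0 for assumed r of 0.25, 0.5 and 0.75. In the simulation with no period effect and r = 0.5, the nominal 5% test rejected in only 0.6% to 0.9% of runs.

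**4. How large is carryover, and where?** Doses from the procedures: bolus 50 cc × 2.5 mg/cc = 125 mg; infusion 2 catheters × 10 cc/h × 2 mg/cc = 40 mg/h. Assume one compartment, immediate absorption and half-life T, and ignore the pre-bolus level. With k = ln 2 / T and h hours of infusion:

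- residual bolus = 125 × 0.5^((4 + h)/T) mg
- infused drug present = (40/k) × (1 − 0.5^(h/T)) mg

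| T (assumed) | At 1 h: residual / infused (mg) | Residual share at 1 h | At 24 h: residual / infused (mg) | Residual share at 24 h |
|---|---|---|---|---|
| 2 h | 22.1 / 33.8 | 39.5% | 0.01 / 115.4 | 0.01% |
| 4 h | 52.6 / 36.7 | 58.9% | 0.98 / 227.2 | 0.4% |
| 6 h | 70.2 / 37.8 | 65.0% | 4.9 / 324.6 | 1.5% |

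At the start of the infusion the model holds 31, 63 or 79 mg (125 × 0.5^(4/T)), below the plateau 40/k of 115, 231 or 346 mg. Drug therefore rises throughout and C_max falls at the 24-hour sample. Infusion coverage is assessed only then. Carryover thus distorts the early infusion curve, not the 24-hour endpoints.

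**5. Can a duration contrast be formed?** Resolution of numbness is followed only up to 4 hours after the bolus. During the infusion there is a single assessment at 24 hours and no offset is recorded, so the logrank test has no infusion-phase event time.

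**6. T_max.** The sampling windows are 10 minutes to 4 hours and 1 to 24 hours, so part of any difference in T_max is set by the schedule.

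**The case against.** The strongest reply is that this is mainly a descriptive pharmacokinetic study. Study design makes serum levels the main measurement and numbness secondary, and for concentration-time curves in one group the no-randomisation sentence is adequate. That stands, and the sentence need not be deleted. But the title, the second aim and Data analysis go beyond description.

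A second reply is that the plan allows for time effects. It delays the study until patients have stabilised after extubation, and expects the 4-hour level to be near or at its pre-bolus value. Both points are fair, but neither removes the aliasing. No pre-bolus sample is listed, so the return to baseline cannot be checked.

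Third, the two phases deliver 125 mg once and 40 mg/h × 24 h = 960 mg, so equal C_max is not expected. The no-regimen-effect simulation is therefore an artificial null. It shows that pairing does not remove confounding; it does not forecast this trial's error rate.

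A reader might also infer that leftover bolus materially biases the infusion C_max and coverage. The documents do not support this. Under the assumptions above, the residual is under 2% of the drug present at 24 hours, when infusion coverage is assessed and the modelled C_max occurs. Nor do they show that drug clearance or catheter position changes between phases. Those changes are possible, but the documents give no size for them.

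**Conclusion.** The point holds for the comparative layer of the plan. Regimen is fully aliased with order and post-operative time, and this rests only on the fixed sequence in the documents. The independent-sample tests are also wrong for same-patient data; the size of that error depends on an unknown within-patient correlation. Carryover matters for the early infusion samples and curve shape: about 40% to 65% of drug present at 1 hour, for assumed half-lives of 2 to 6 h, one compartment and immediate absorption. It is not a material bias in 24-hour coverage or in a C_max reached at 24 hours. The logrank comparison cannot be carried out as scheduled.

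The first aim is unaffected. It would go too far to conclude that the study needs randomisation or that its curves are invalid: the design supports description of each phase, but not a claim of regimen effect. The change should be made before analysis.

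**What to change.** Treatment order and dosing stay as they are.

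1. In the title, aims and Data analysis, replace arm wording with phase and describe a single-group, fixed-sequence study. Keep the no-randomisation sentence only as the rationale for the descriptive aim.
2. Make per-phase pharmacokinetic parameters and dermatomal coverage, with 95% CIs, the main results.
3. Replace the unpaired t-test and the Kolmogorov-Smirnov test with within-patient differences or ratios and 95% CIs. Label them descriptive, and state that regimen cannot be separated from order and post-operative time. Give the sampling windows beside any T_max contrast.
4. Drop the logrank comparison and report duration of numbness for the bolus phase only.
5. Use the already planned 4-hour bolus sample as the time-zero value of the infusion phase, so that the early infusion curve is read against the level it started from.

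The cost is that the comparative p-values are given up and the approved analysis section must be amended. No extra sample or visit is needed.

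### The outcome labelled duration of analgesia is self-reported numbness, so it can support a statement about sensory block but not about how long pain relief lasts

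*Combined protocol and SAP*

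**What the plan says.** The Combined protocol and SAP uses two terms for one secondary outcome.

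Three places say analgesia. The second aim, under Specific aims of the project, is: "Determine the dermatomal distribution and duration of analgesia created when ESP block is performed via ropivacaine bolus versus continuous ropivacaine infusion". Research protocol, part 1 labels the outcome in the same way: "the secondary outcome of dermatomal analgesia and duration will be assessed". The Data analysis section applies a logrank test to "the duration of analgesia created by the bolus arm and the infusion arm".

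Two places say numbness. Significance of the research says that the study "will also assess for areas of numbness created by the ESP block when routine doses are administered". Study design says: "Secondary measurements will include distribution and duration of numbness created by the ESP block".

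The measurements are in Description of procedures. At 60 minutes after the bolus an investigator will "test areas of numbness performing a pinprick test and using a dermatomal map to mark the areas of numbness". At the three later contacts the participant is only asked whether the numbness has ended, and gives a remembered clock time if it ended between contacts. Research protocol, part 2 has one dermatomal analgesia assessment at 24 hours of infusion and states no method for it.

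**The concern.** Loss of sharp sensation on the skin and relief of pain after cardiac surgery are different quantities. As a matter of general clinical reasoning, pain from deep structures or drain sites can persist under numb skin, and a patient can be comfortable with patchy numbness. The documents do not say how often the two diverge. They also do not define analgesia or say that numbness stands in for it.

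The setting invites the clinical reading. The Background presents the block as a way to control pain in thoracic surgery, and Significance of the research discusses the volume needed to produce analgesia. A reader who meets a duration of analgesia in postoperative cardiac patients will probably take it as duration of pain relief. If the plan is followed as written, a time to loss of numbness would be reported under that name, with a bolus-versus-infusion comparison attached to it. This affects one of two aims and one of the three tests in the Data analysis section.

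**Working it through.** The documents give no sample size, effect size or other figure for this outcome, so there is no number to reproduce. The check compares each name for the outcome with each measurement planned for it.

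**Measurements planned (Research protocol, parts 1 and 2)**

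| Phase | Time | What is recorded | Pain or analgesic use |
|---|---|---|---|
| Bolus | 60 min | Pinprick dermatomal map | None |
| Bolus | 90 min | Question: has numbness gone? | None |
| Bolus | 2 h | Same question | None |
| Bolus | 4 h | Same question | None |
| Infusion | 24 h | Dermatomal assessment, method not stated | None |

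**Counts**

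- Sensory contacts: 4 in the bolus phase + 1 in the infusion phase = 5.
- Observation time: 4 h + 24 h = 28 h.
- Planned pain scores or analgesic-use measures: 0.
- Time-to-resolution variables: 1 in the bolus phase (self-reported numbness, followed to 4 h) and 0 in the infusion phase.

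**Two readings of analgesia**

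1. *Clinical pain relief.* Nothing recorded measures it, so neither its distribution nor its duration can be reported.
2. *Loss of sharp sensation by dermatome.* The pinprick test uses "a pointed object that is sharp enough to elicit a sharp sensation but blunt enough that it does not cause skin damage" and compares skin expected to be numb with skin that is not. The 60-minute map therefore supports a statement on distribution. It does not support one on duration, because pinprick is not repeated at 90 minutes, 2 hours or 4 hours. The duration variable is the participant's report that numbness has ended.

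Under either reading, the duration variable is self-reported numbness. It is neither pain relief nor pinprick loss.

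**The case against.** The strongest reply is that the plan is open about what it measures. Its title speaks of dermatomal coverage, and both Significance of the research and Study design call the outcome numbness. Pain relief is not itself listed as an aim. The sentence that labels the outcome dermatomal analgesia is followed at once by the pinprick method, so in context the phrase can mean loss of sharp sensation by dermatome. Pain scores would also be new outcomes in a pharmacokinetic and dermatomal study. With a fixed bolus-then-infusion order and no concurrent control, they would be mixed with time since surgery and with other analgesics.

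Most of this stands. It shows the likely intent, makes renaming a sufficient minimum, and makes pain scores optional. It does not rescue the duration label, since pinprick is not repeated.

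A reader might infer that the trial can say nothing about analgesia, or that the second aim cannot be answered because of the label. The documents do not support either inference. The 60-minute map permits a limited statement on pinprick loss, and the distribution part of the aim has an assessment in each phase.

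A reader might also infer that correcting the label would make the logrank comparison valid. It would not. The single 24-hour assessment gives no infusion duration under any name. The two arms are also the same participants in sequence, which a standard logrank test for independent groups does not fit.

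**Conclusion.** The point holds as a fault of definition and labelling in a secondary outcome. The data can support the dermatomal distribution of pinprick loss and the duration of self-reported numbness after the bolus, observed to 4 hours. They cannot support a statement on the duration of postoperative pain relief, because none of the 5 planned sensory contacts records pain or analgesic use. The conclusion rests on the procedures as written, and on the 24-hour assessment being sensory, as its name and its place in the plan suggest. It does not depend on how often numbness and pain relief diverge, which the documents do not quantify. The change is worth making because the outcome serves one of only two aims and the minimum correction is one of wording.

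**What to change.** 1. **Rename the outcome.** Use distribution and duration of cutaneous sensory block (numbness) in the second specific aim, in Research protocol, parts 1 and 2, and in Data analysis. State that distribution comes from pinprick and duration from self-report, and limit the conclusion to sensory block. The cost is a narrower headline claim.

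2. **Only if a statement about analgesia is intended, measure it.** Record a 0-10 pain score at six existing bedside contacts: the verbal reaffirmation before the bolus, then 60 minutes, 90 minutes, 2 hours, 4 hours and 24 hours of infusion. Abstract concurrent analgesic use from the chart. Report both descriptively, with pain as within-patient change from the pre-bolus score, and state the fixed order and the lack of a concurrent control. No new visit or staff is needed. The burden is an assumed minute or so per contact plus some chart abstraction. The pre-bolus contact has no outcome assessment at present, so the score there is a small addition.

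3. **Correct the logrank comparison separately.** It needs either an infusion-phase time to resolution with a method suited to paired data, or withdrawal of the duration comparison in favour of a description of the bolus phase alone.

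### The infusion curve starts a fixed 4 hours after the 125 mg study bolus with no planned correction, so any remaining bolus drug counts as early infusion exposure; C_max and T_max are little affected

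*Combined protocol and SAP*

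**What the plan says.** The first specific aim is to "Create plasma ropivacaine concentration-time curves after performance of an ESP block via bolus and continuous infusion into the ESP compartment", and the aim says that these curves will include C_max and T_max. Description of procedures closes with the same intention: "creation of a pharmacokinetic profile for the ESP block (both bolus and infusion curves").

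Every participant receives both treatments in a fixed order. In part 1, "the investigator will administer 25 cc 0.25% ropivacaine through each nerve catheter (totaling 50 cc 0.25% ropivacaine"), with samples from 10 minutes to 4 hours afterwards. Part 2 is tied to the clock: "at the 4-hour interval (4 hours after the initial bolus), both nerve catheter infusions will be resumed". Infusion samples follow at 1, 2, 4, 8, 12 and 24 hours. The basis for the 4-hour gap is one sentence, which begins: "It is expected that at the 4-hour interval, the serum ropivacaine level will be approaching or have reached the baseline level before the bolus was". The plan offers no half-life, threshold or check in support.

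Data analysis names a Kolmogorov-Smirnov test between the bolus and infusion arms, unpaired t-tests on T_max and C_max, and a logrank test on duration. It does not mention residual drug.

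**The concern.** The expectation allows for a level that is only approaching baseline, so the plan itself leaves room for bolus drug at the moment the infusion begins. Whatever remains is present in the part 2 samples. The analysis section counts those samples as infusion data without separating the two sources. The early infusion curve would then be a falling bolus plus a rising infusion. This would be so even if no test between the arms were done.

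At stake is the early shape of the infusion curve, roughly hours 1 to 8. The Introduction asks how quickly, as well as how closely, toxic levels are reached. A reader who takes the part 2 curve as infusion alone would misjudge how fast an infusion raises the level.

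**Working it through.** The plan states no expected concentration, half-life or carry-over figure, so there is none to reproduce. The check uses the plan's doses and times with assumed kinetics.

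**Inputs from the documents**
- Bolus (part 1): 2 x 25 mL = 50 mL at 2.5 mg/mL = 125 mg.
- Infusion (part 2): "both nerve catheter infusions will be resumed at a concentration and rate of 0.2% ropivacaine at 10 cc/hr". At 2 mg/mL this is 2 x 10 x 2 = 40 mg/h if the rate applies to each catheter, or 10 x 2 = 20 mg/h if it is the total. The text does not say which.
- Gap: 4 hours. Infusion samples at t = 1, 2, 4, 8, 12 and 24 h are therefore 5 to 28 h after the bolus.

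**Assumed inputs**
- Linear one-compartment model with first-order absorption.
- Elimination half-life 2, 4, 6 or 8 h, and absorption half-life 0.25 or 1 h. A faster case (1 h and 0.25 h) is added.
- The keep-open infusion is left out at this step.

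**Formulas**
- With k = ln 2 / elimination half-life and ka = ln 2 / absorption half-life, f(t) = ka/(ka - k) x [exp(-kt) - exp(-ka t)].
- Bolus drug in the body at infusion time t: B(t) = 125 x f(t + 4).
- Infused drug: I(t) = R x integral of f from 0 to t, with R = 40 or 20 mg/h.
- Bolus share = B/(B + I). Volume of distribution cancels.

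**Worked values at infusion hour 1, R = 40 mg/h**
- Half-lives 2 h and 0.25 h: B = 25.3 mg, I = 23.2 mg, share 25.3/48.5 = 52%.
- Half-lives 8 h and 1 h: B = 88.2 mg, I = 10.8 mg, share 88.2/99.0 = 89%.

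**Bolus share of the measured level**

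| Infusion hour | 40 mg/h, assumed range | 20 mg/h, assumed range | 40 mg/h, faster case |
|---|---|---|---|
| 1 | 52-89% | 69-94% | 20% |
| 2 | 27-71% | 42-83% | 6% |
| 4 | 10-43% | 18-60% | 1% |
| 8 | 2-20% | 4-34% | about 0% |
| 12 | 0-11% | 1-21% | about 0% |
| 24 | at most 3% | at most 6% | about 0% |

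**Effect on the planned parameters.** Over the assumed range the highest infusion-period level is at 24 h with or without the residual, so T_max does not move. Sampled C_max rises by at most about 3% at 40 mg/h and about 6% at 20 mg/h.

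**The 4-hour level.** It is 39-100% of the highest sampled bolus value over the assumed range, and about 13% in the faster case. With a 6 or 8 h elimination half-life and 1 h absorption, the highest sampled bolus value is the 4-hour sample itself.

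**Keep-open infusion.** Before the bolus the catheters run at 1 cc/hr. Assuming 0.2% through two catheters (2 x 1 x 2 = 4 mg/h) for 20 h, the drug left from this source 4 h after the bolus is 9-33% as large as the bolus residual over the 2-8 h range.

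**The case against.** The strongest objection is that the size of the effect is assumed. The documents give no kinetics, and the faster case, which is closer to the protocol's own expectation, leaves 6% at hour 2 and 1% at hour 4. If levels really are back at baseline by 4 hours, the effect is negligible. This stands: what the documents establish is the missing correction, not its magnitude.

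The hour-1 percentages are also large partly because an infusion has delivered little by then. Set against the 24-hour infusion level, the hour-1 residual is about 21-32% at 40 mg/h. That puts the figure in proportion but does not remove it, since the early rise is what the curve is meant to show.

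Four stronger readings are tempting, and the documents do not support them:
- A reader might infer that infusion C_max and T_max are contaminated, since the aim names them and Data analysis tests them. The model shows almost no movement in either.
- A reader might infer that the plan commits to plotting uncorrected values. It says only that the data can be used to build the profile; the absence of a correction is silence.
- A reader might infer that the 4-hour sample tests the washout. It gives the level at infusion start, but no pre-bolus sample is listed, so the baseline in question is not measured.
- A reader might infer that everything left at 4 hours is bolus drug, or that the curve should start at zero. The keep-open infusion, and possibly the pre-operative block, also contribute.

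**Conclusion.** The point holds for the early infusion curve. The start of part 2 is fixed by time, the washout behind it is an unverified expectation, and nothing in Data analysis separates remaining bolus drug from infused drug. Under the assumed linear model the distortion is large at hours 1 to 4, smaller at hour 8 and small by 24 h. It is greater if 10 cc/hr is the total rate and much smaller if absorption and elimination are fast. The planned infusion C_max and T_max are little affected. This is a weakness in how half of the first aim would be reported, and it can be corrected in the analysis.

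**What to change.** Keep the schedule and samples, and add the following to Data analysis:

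1. Use the 4-hour post-bolus sample as the time-zero value of the infusion curve. Report it for each patient as an absolute level and as a percentage of bolus C_max.
2. Beside the observed curve, present an infusion-only curve obtained by superposition, using actual dosing and sampling times. Either subtract each patient's extrapolated bolus decline or fit both phases jointly. Where the bolus curve has not turned down by 4 hours there is no decline to extrapolate, and the joint fit is needed. Include the 1 cc/hr keep-open infusion as an input, with its concentration and running time recorded.
3. Label the observed part 2 curve as an infusion started 4 hours after a 125 mg bolus. Use the 24-hour sample as the model-free description of infusion alone. The 12-hour sample is less suitable, because it may still carry up to 11% bolus drug (21% at 20 mg/h).
4. Do not claim that levels returned to baseline, since no pre-bolus sample is listed.

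The text should also state whether the 10 cc/hr applies to each catheter or in total, because the model needs it.

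The cost is a few lines of analysis text and modest modelling, with no extra blood, patients or change in care. The downside is that the early infusion-only curve becomes model-based and depends on the fit.
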